10.2. Baseline Demographics

Patient characteristics will be summarised by treatment arm, for each of the analysis populations defined above (Section 10.1). Summaries of continuous variables will be presented as means and standard deviations if normally distributed, and as medians and inter-quartile ranges for skewed data; categorical variables will be presented as frequencies and percentages.

10.3. Analysis Summary

End Points	Outcome/Variable	Analysis	Population
Feasibility and	Recorded data on	Mean number of	All randomised
acceptance of	whether patients have	patients recruited per	patients before
randomisation	been (CONSORT):	month per centre	Covid-19
(rate per-month per-centre	RecruitedEnrolled and	Recruitment rate	. All roadonsies d
averaged) and	 Enrolled and consented 	 Graph displaying recruitment rate over 	 All randomised patients during/after
compliance to	Randomised	time	Covid-19
allocated arm	Withdrawn/Lost to	Graph of actual vs	
	follow-up	target recruitment	
	 In follow-up (and 	rate over time	
	what stage of follow-		
	up)	Mean number of	
	Completed	patients randomised per month per centre	
		Randomisation rate	
		Graph displaying	
		randomisation rate	
		over time	
	Days between	Summary statistics for	
	consent and	time between consent and randomisation	
	randomisation	and randomisation	
		Reasons for ineligibility	
	Reasons for Reasons for Reasons fo	,	
	ineligibility		
	 Days between 	Summary statistics for	Patients who started
	randomisation and	time between	treatment before
	start of treatment	randomisation and treatment	Covid-19 • Patients who started
	 Days between randomisation and 	Summary statistics for	Patients who started treatment
	start of neoadjuvant	time between	during/after Covid-
	drug treatment	randomisation and start	19
	(CHRONOS-B)	of neoadjuvant	
	Days between start of	treatment (CHRONOS-	
	neoadjuvant drug treatment and start of	B only) Summary statistics for	
	focal therapy	time between start of	
	(CHRONOS-B)	neoadjuvant treatment	
	Treatment details (as	and start of focal	
	recorded at Visit 2)	therapy (CHRONOS-B	
		only)	
		Treatment compliance:	

Imperial Clinical
Trials Unit

STATISTICAL ANALYSIS PLAN: FEASIBILITY

CHRONOS

 Treatment details (as recorded at Visit 2/3) Protocol deviations for treatment compliance 	 Proportions of patients who underwent their allocated treatment (Visit 2) Drug compliance (CHRONOS-B only): Proportions of patients returned their empty blister packs (yes/no) (recorded at Visit 3) Proportions of patients who were given the drug and do not have a registered protocol deviations stating that the drug was taken for less than 8 weeks 	 Patients who started neoadjuvant drug treatment before Covid-19 (CHRONOS-B only) Patients who started neoadjuvant drug treatment during/after Covid-19 (CHRONOS-B only)
Date of visit	Summary statistics for time between consecutive visits	 Patients who underwent their most recent of the consecutive visits before Covid-19 Patients who underwent their most recent of the consecutive visits during/after Covid-19
Date of visit	Proportions of patients with missing or delayed visits	 Patients who underwent the visit before Covid-19 Patients who underwent the visit during/after Covid-19
Reasons for withdrawal	Reasons for withdrawal	 Patients who withdrew before Covid-19 Patients who withdrew during/after Covid-19

All analyses will be repeated for CHRONOS-A and CHRONOS-B separately.

10.4. Analysis of End Points

The following analyses will be conducted separately for each of the two patient populations defined in the table above (Section 10.3).

STATISTICAL ANALYSIS PLAN: FEASIBILITY

CHRONOS

The mean number of patients recruited and randomised per month, per centre (including only the months in which the centre is open and recruiting), will be calculated. Overall recruitment and randomisation rates will also be calculated, along with their corresponding 95% confidence intervals. Recruitment rate is calculated as the number of participants recruited out of the total number approached. Randomisation rate is calculated as the number of participants randomised out of the total number recruited. Graphs displaying the recruitment and randomisation rates over time will be presented. A graph displaying the actual vs target recruitment rates will also be presented. These analyses will be conducted for CHRONOS-A and CHRONOS-B.

Compliance will be summarised using summary statistics, by treatment arm, for the time between consecutive visits, from screening visit to final follow-up visit (Visit 3 for feasibility phase). The proportions of patients, in each treatment arm, with a missing or delayed visit will also be presented. A missed visit is a visit at which no information was collected. A delayed visit is a visit which is outside of the visit window defined in the Visit Schedule (Section 6.7.2). These statistics will be presented for CHRONOS-A and CHRONOS-B.

Summary statistics for time between consent and randomisation, and randomisation and treatment will be presented by treatment arm. Summary statistics will also be presented for time between consecutive visits, by treatment arm.

For CHRONOS-B only, summary statistics will also be presented for time between randomisation and start of neoadjuvant treatment, and time between start of neoadjuvant treatment and start of focal therapy.

Treatment, for CHRONOS-A and CHRONOS-B, is recorded at Visit 2 (Treatment Visit). For focal therapy arms (CHRONOS-A (Focal arm) and CHRONOS-B) treatment is recorded by date of treatment and completed treatment details at Visit 2. For the radical arm of CHRONOS-A, treatment is recorded by date of visit 2 and completed treatment details on Radiotherapy/Brachytherapy Log and Prostatectomy Log at Visit 2. The proportions of patients in each treatment arm who underwent treatment will be presented, along with their corresponding 95% confidence intervals.

Treatment compliance will be evaluated by arm and by trial (CHRONOS-A/CHRONOS-B). Viable treatment compliance is defined as the lower end of the confidence interval for the proportion of patients who underwent treatment being $\geq 80\%$. If the lower end of the confidence interval for the proportion of patients who underwent treatment is $\geq 80\%$, then we have viable compliance to progress to the main phase. If the lower end of the confidence interval for the proportion of patients who underwent treatment is between 70% and 80%, then this indicates that remedial work is needed to improve this for the main stage. If the lower end of the confidence interval for the proportion of patients who underwent treatment is < 70%, then this could affect the primary outcome analysis and threaten the validity of the study. Data will be presented to the TSC for a final decision in this case.

Neoadjuvant drug treatment in CHRONOS-B is prescribed at randomisation. Drug compliance will be estimated using two definitions:

- Patients who returned their empty blister packs (yes/no) at Visit 3
- Patients who took the drug and did not have a registered protocol deviation stating that they took the drug for less than 8 weeks.

For CHRONOS-B only, the proportions of patients who returned their empty blister packs (yes/no), and the proportions of patients who took the drug and did not have a registered protocol deviation stating that they took the drug for less than 8 weeks, in each treatment arm will be reported, along with their corresponding 95% confidence intervals. Drug compliance will be evaluated by arm and by trial for each of the drug compliance definitions. Viable drug compliance is defined as the lower end of the confidence interval for the proportions being \geq 90%. If the lower end of the confidence interval for the proportions is between 80% and 90%, then this indicates that remedial work is needed to improve this for the main stage. If the lower end of the confidence interval for the

CHRONOS

proportions is < 80%, then this could affect the primary outcome analysis and threaten the validity of the study, and may require sample size re-estimation. Data for both drug compliance definitions will be presented to the TSC for a final decision in this case.

The reasons for ineligibility and withdrawal will be collected and recorded for CHRONOS-A and CHRONOS-B separately.

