8.2 Planned recruitment rate

Within the UK approximately 10,000 patients meeting our eligibility criteria undergo radical therapy a year and 700 patients undergo FT. Thus, the potential pool of eligible patients is large and the timeline to full accrual is based on UK estimates and would allow both CHRONOS-A and CHRONOS-B to complete recruitment within 5 years and primary outcome analysis to occur after 8 years. For the pilot stage 120 patients (60 each for CHRONOS-A and CHRONOS-B) will be recruited from approximately 6 sites over 12-months. The pilot will assess feasibility of our recruitment timelines and final recruitment rates will be based on the data from the pilot.

The recruitment rate will be assessed as part of our pilot and timelines for the main stage will be adjusted accordingly. In order to allow the majority of UK sites to be eligible for the study, we will develop a centralised process for the delivery of trial therapies/interventions. In brief, if a site does not have direct access to either FT or radiotherapy or surgery then there will be a process in place for the treatment to take place in a nearby trial site that offers that treatment.

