9.3. Primary End Point Analysis

The proportions of patients who opted for CHRONOS-A and CHRONOS-B will be reported.

The primary analysis of the internal pilot will calculate the mean number of patients recruited and randomised per month, per centre (including only the months in which the centre is open and recruiting). Overall recruitment and randomisation rates will also be calculated, along with their corresponding 95% confidence intervals. Recruitment rate is calculated as the number of participants recruited out of the total number approached. Randomisation rate is calculated as the number of participants randomised out of the total number recruited. Graphs displaying the recruitment and randomisation rates over time will be presented. A graph displaying the actual vs target recruitment rates will also be presented. These analyses will be conducted for CHRONOS-A and CHRONOS-B.

Compliance will be summarised using the CONSORT diagram for the internal pilot (see Section 1.1.1) which includes, the number of men who have withdrawn or been lost to follow-up (with reasons), and the number who completed each stage within each treatment arm. There will be a separate CONSORT for CHRONOS-A and CHRONOS-B.

Summary statistics for time between consent and randomisation, and randomisation and treatment will be presented by treatment arm. Summary statistics will also be presented for time between consecutive visits, by treatment arm.

For CHRONOS-B only, summary statistics will also be presented for time between randomisation and start of neoadjuvant treatment, and time between start of neoadjuvant treatment and start of focal therapy.

Treatment, for CHRONOS-A and CHRONOS-B, is recorded at Visit 2 (Treatment Visit). For focal therapy arms (CHRONOS-A (Focal arm) and CHRONOS-B) treatment is recorded by date of treatment and completed treatment details at Visit 2. For the radical arm of CHRONOS-A, treatment is recorded by date of visit 2 and completed treatment details on Radiotherapy/Brachytherapy Log and Prostatectomy Log at Visit 2. The proportions of patients in each treatment arm who underwent treatment will be presented, along with their corresponding 95% confidence intervals.

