9.5. Impact of the Covid-19 Pandemic

To assess the impact of the Covid-19 pandemic on the feasibility phase of the trial, we will assess the baseline demographics, recruitment rate, randomisation rate, reasons for ineligibility, and time between consent and randomisation to see if there exist important differences between the population recruited before the Covid-19 pandemic and the population recruited during/after the Covid-19 pandemic.

Time between randomisation and treatment, treatment compliance (CHRONOS-A and CHRONOS-B) and drug compliance (CHRONOS-B) will be assessed between the population who

Imperial Clinical
Trials Unit

STATISTICAL ANALYSIS PLAN: FEASIBILITY

CHRONOS

underwent treatment before the Covid-19 pandemic and those who underwent treatment during/after the Covid-19 pandemic.

Time between consecutive visits will be assessed between the population who underwent their most recent consecutive visit before the Covid-19 pandemic and those who underwent their most recent consecutive visit during/after the Covid-19 pandemic. Similarly, proportions of patients with missing or delayed visits will be assessed between patients who underwent that visit before the Covid-19 pandemic and those who underwent that visit during/after the Covid-19 pandemic.

Reasons for withdrawal will be assessed between the population who withdrew before the Covid-19 pandemic and the population who withdrew during/after the Covid-19 pandemic.

Trial processes and conduct will also be assessed for important differences between these populations. This analysis is detailed further in Section Error! Reference source not found.

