10.1. Analysis Populations

On 05/03/2020, Covid-19 was added to Public Health England's list of notifiable diseases in England and Wales (11).

Analysis Population	Population Definition	End Points
Patients randomised	Patients randomised to the trial	Baseline demographics
before the Covid-19 pandemic	before 05/03/2020	 Recruitment rate Reasons for ineligibility
 Patients randomised during/after the Covid-19 pandemic 	Patients randomised to the trial on/after 05/03/2020	Time between consent and randomisation
 Patients who underwent radical or focal treatment before the Covid-19 pandemic 	Patients whose radical or focal treatment start date is before 05/03/2020	 Time between randomisation and treatment Treatment compliance
Patients who underwent radical or focal treatment during/after the Covid-19 pandemic	Patients whose radical or focal treatment start date is on/after 05/03/2020	(CHRONOS-A and CHRONOS-B)
Patients who started neoadjuvant drug treatment before the Covid- 19 pandemic	 Patients whose neoadjuvant drug treatment start date is before 05/03/2020 (CHRONO- B only) 	Drug compliance (CHRONOS-B)
 Patients who started neoadjuvant drug treatment during/after the Covid-19 pandemic 	Patients whose neoadjuvant drug treatment start date is on/after 05/03/2020 (CHRONOS-B only)	
Patients who underwent their most recent consecutive visits before the Covid-19 pandemic	 Patients whose most recent date of visit is before 05/03/2020 	Time between consecutive visits
 Patients who underwent their most recent consecutive visits during/after the Covid-19 pandemic 	Patients whose most recent date of visit is on/after 05/03/2020	
 Patients who attended the visit in question before Covid-19 pandemic 	Patients whose date of visit is before 05/03/2020	 Proportions of patients with missing or delayed visits
 Patients who attended the visit in question after the Covid-19 pandemic 	Patients whose date of visit is on/after 05/03/2020	
 Patients who withdrew from the trial before the Covid- 19 pandemic 	Patients whose withdrawal date if before 05/03/2020	Reasons for withdrawal
 Patients who withdrew during/after the Covid-19 pandemic 	Patients whose withdrawal date is on/after 05/03/2020	

The following analyses will only be presented is there exist patients in both the before and during/after Covid-19 pandemic populations. Analyses for populations which do not contain any patients will be omitted as they are already included in the main analysis outlined in Section 9.

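### The Covid-19 comparison of recruitment per centre-month counts only open months, so it cannot show accrual lost while a centre was suspended

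*SAP*

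**What the plan says.** SAP 9.5 introduces the pandemic analysis with this purpose: "To assess the impact of the Covid-19 pandemic on the feasibility phase of the trial". Recruitment is among the features to be compared: "we will assess the baseline demographics, recruitment rate, randomisation rate, reasons for ineligibility, and time between consent and randomisation". The dividing date is set in SAP 10.1: "On 05/03/2020, Covid-19 was added to Public Health England's list of notifiable diseases in England and Wales".

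SAP 10.4 then specifies the figures, separately for each period. Average numbers recruited and randomised "per month, per centre (including only the months in which the centre is open and recruiting), will be calculated". Tables 6.1 and 6.2 hold the results. The main pilot analysis in SAP 9.3 (Table 2.2) has the same restriction, "including only the months in which the centre is open and recruiting". The SAP does not say how a paused centre, or an open month with no recruit, is to be counted.

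The second measure is a proportion: "Recruitment rate is calculated as the number of participants recruited out of the total number approached". Tables 6.3 and 6.4 give it by period with numerator and denominator, following the layout of Table 2.3. SAP 10.8 lists graphs of recruitment rate, and of actual against target recruitment rate, over time in each period. No listed table gives open or suspended centre-months, or a rate on calendar time.

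Protocol 8.2 looks ahead to the main stage: "final recruitment rates will be based on the data from the pilot".

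**The concern.** A pandemic can reduce accrual in two ways. Centres that stay open may recruit more slowly, or centres may stop recruiting for a time. A rate per open month measures only the first. When a centre is paused, its recruits (none) and its months (not counted) both drop out of the calculation, so the average stays where it was.

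The comparison could therefore report the same recruitment per centre-month before and after 05/03/2020 when a substantial part of the later period produced no recruits. A reader of Tables 6.1 and 6.2 could take that as evidence that the pandemic did not affect recruitment. The figure also matters later, because main-stage timelines run on calendar time and protocol 8.2 says they will be adjusted in the light of the pilot.

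**Working it through.** **Inputs.** SAP 6.6.1 and 6.6.2 (and protocol 8.1.1) expect 60 patients per trial from 6 centres in 12 months. The denominator rule is in SAP 10.4. The documents give no number or length of suspensions, so the number of suspended months, *s*, is assumed and varied. The illustration takes a 12-month period after the cut date, the same *s* in all 6 centres, and an unchanged pace in open months.

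**The plan's own figures.** The planned pace is 60/(6 × 12) = 60/72 = 0.833 per centre-month. SAP section 11 gives a 95% interval for a 33% recruitment rate with 60 participants. The normal approximation, 0.33 ± 1.96 × √(0.33 × 0.67/60), gives 0.211 to 0.449, which matches. That interval concerns recruited out of approached, so the progression rule built on it contains no unit of time.

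**Formulas.** With *T* = 12 calendar months:

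- Recruits = 0.833 × 6 × (*T* − *s*)
- SAP rate = recruits / [6 × (*T* − *s*)]
- Calendar rate = recruits / (6 × *T*)

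**Results.**

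| Suspended months (assumed) | Recruits | SAP open-month rate | Calendar rate | Change in calendar rate |
|---|---|---|---|---|
| 0 | 60 | 60/72 = 0.833 | 60/72 = 0.833 | 0% |
| 3 | 45 | 45/54 = 0.833 | 45/72 = 0.625 | −25% |
| 6 | 30 | 30/36 = 0.833 | 30/72 = 0.417 | −50% |

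The SAP rate is the same in every row. The calendar rate falls by the fraction *s*/*T*. Put as time, six centres would need 12 + *s* months to reach 60, that is 12, 15 or 18 months.

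**Contrast with a slowdown.** If no centre pauses but intake halves, recruits are 30 over 72 open centre-months. Both rates are then 30/72 = 0.417, so the SAP rate does register this loss. The last row of the table and this case both end with 30 men in 12 months, yet Tables 6.1 and 6.2 would show no change in one and a halving in the other.

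**Whether other outputs recover the loss.** Recruited out of approached does not, because a paused centre adds nothing to either count. The period counts in Tables 6.3 and 6.4 would be lower after a pause, but turning them into a rate needs the length of each period and the dates when each centre was active, which no table supplies. A graph of cumulative recruits against target on a calendar axis would show a pause. However, 10.4 defines recruitment rate as a proportion, and the SAP does not say that the graphs will plot counts.

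**The case against.** The strongest reply is that an open-month rate is a legitimate measure. It suits staggered site opening and estimates what a centre delivers when it is active. The information is also not wholly lost. Counts recruited and approached appear by period in Tables 6.3 and 6.4. SAP 8.3 lists monthly numbers by centre without the open-month restriction. The actual-against-target graph may show a gap. Section 10 also covers treatment delays, missed or delayed visits, withdrawals and Covid-19 protocol deviations. All of this stands, and it limits the point to the per-centre-month comparison. It does not answer that point, because none of these outputs is specified as an analysis of accrual per unit of calendar time.

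A reader might go further and infer that suspension was the pandemic's main effect on this trial. The documents do not say that any centre was suspended, or for how long, so that cannot be concluded. A reader might also take "including only the months in which the centre is open and recruiting" to exclude every month without a recruit, which would inflate the average. The phrase more naturally describes the status of a site, and the documents do not support building a figure on the other reading. Finally, a reader might suppose that the open-month rate will pass unadjusted into the main-stage timeline. Protocol 8.2 says only that pilot data will be used. Relying on the calendar rate alone would have its own fault, since it could project a one-off pause over a five-year recruitment period.

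**Conclusion.** The point holds for Tables 6.1 and 6.2. As specified, they cannot show accrual lost to suspended centres, although SAP 9.5 sets out to assess the pandemic's impact on recruitment. The size depends on how much time was suspended, which the documents do not give. On the stated assumptions, 3 or 6 suspended months out of 12 leave the SAP figure at 0.83 while calendar accrual per centre-month falls to 0.63 or 0.42. If no centre was paused, the two rates agree and nothing is hidden. The comparison also arises only if both periods contain patients, as SAP 10.1 requires.

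It would be wrong to say that the whole Covid-19 analysis is blind to the pandemic, since a slowdown at open centres remains visible. Nor does any progression decision change: section 11 uses recruited out of approached against 21.1% and 33%. The gap is in a descriptive comparison, but one that can give a misleading answer to the question it was written to address.

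**What to change.** In SAP 10.4 (Tables 6.1 and 6.2), and beside Table 2.2 in SAP 9.3, add recruits and randomisations per calendar centre-month. Count from site activation to the end of pilot recruitment, including suspended months and open months with no recruit. For the Covid-19 tables, split the time at 05/03/2020 and report the open and suspended centre-months in each period.

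Use the calendar rate for the before/after comparison. Keep the open-month rate as the measure of capacity, and state that an open month with no recruit counts as zero. Show both rates when main-stage timelines are set under protocol 8.2, so that whoever sets them can judge how far a past pause should be projected forward.

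The cost is a few lines of SAP text and one extra column, from site activation and suspension dates. The calendar rate may look less favourable than the open-month rate.

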6.7.2. Visit Schedule

The design and number of visits mirror the standard of care pathway for patients undergoing either focal therapy or radical therapy, so that additional patient burden is minimal. Prior to enrolment, all patients will have undergone a Prostate Specific Antigen (PSA) blood test, a diagnostic prostate MRI and prostate biopsies. A standard of care (SOC) multi-disciplinary team case review will precede any discussion with the patient on all suitable treatment options and trial suitability. After an MDT discussion confirming suitability for FT and/or radical therapy has taken place, a patient information sheet (PIS) explaining the study will be provided, after which patients will be given a minimum of 24 hours to consider taking part. We aim for consent to be taken during a SOC appointment, or an additional consultation via phone, or in person. Randomisation will take place during the visit in which consent is taken along with any required neoadjuvant therapy, as allocated via randomisation, to be prescribed and within 24 hours of receiving the prescription. Time from randomisation will be used to define progression free survival and failure free survival. The end of treatment is defined as the final part of any intervention. For radiotherapy, this is the final radiation fraction completed and for prostatectomy and focal therapy the point at which the catheter is removed. Therefore, the follow-up visits noted below will start from these time-points, which will define the date of first follow-up visit (visit 2).

	Screening & Consent	Visit						
Visit	1	2	3	4	5	6	7	6 monthly visits until last visit 60 months after visit 2
Months				se below spec ach arm	ify the	e mon	ths af	ter the completion of each treatment
		0	3	12	18	24	30	31-60. Visits 4 onwards can be telephone consultations in order to note clinical outcomes although MRI scans and biopsies where done will require physical visits to the hospital
Informed Consent and enrolment into either CHRONOS A or CHRONOS B	Х							
Inclusion & exclusion criteria checked, including concomitant medication review	х							
Randomisation	x							
Prescription of neo- adjuvant therapy	X (if randomised to such arm)							Within 24hrs of randomisation
PSA blood test			Х	Х	Х	Х	Х	X (6 monthly)
Prostate Contrast MRI	X (if randomised to focal therapy and no contrast given during diagnostic scan – to have prior to visit 2)							
Prostate mpMRI				X (focal therapy arms)				

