Biopsy				X (focal therapy arms)				
Treatment		X (these vary in length)						X (focal therapy arms – a second treatment will be permitted for a histologically confirmed recurrent, residual or new out-of-field disease)
Clinical assessment (optional, only if required)			Х	Х	х	х	Х	
PROMS questionnaires	Х		х	х		х		X (every 12 months, at 24, 36, 48 and 60 months visits)

Imperial Clinical Trials Unit	STATISTICAL ANALYSIS PLAN: FEASIBILITY	CHRONOS
----------------------------------	--	---------

[figure not shown]
Review/ reporting of patient AEs/SAEs		Х	Х	Х	Х	Х	Х	Х
Blood and urine tests including those for biobanking (optional)	Х		Х	Х				X

Time window for each visit will be +/- 4 weeks

Minimum length of follow up for the pilot will be 3 months from treatment for each patient. Then treatment will revert to standard of care.

[figure not shown]

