Table 6. 19: Summary statistics of time between consecutive visits (Days) from Screening Visit 1 to Visit 4², by treatment arm, for patients who underwent the most recent of the consecutive visits before¹ the Covid-19 pandemic (CHRONOS-B)

See output for Table 2. 7, but for patients in CHRONOS-B who underwent the most recent of the consecutive visits before¹ the Covid-19 pandemic.

¹Patients underwent the most recent of the consecutive visits before the Covid-19 pandemic if the date of visit of their most recent consecutive visit was before 05/03/2020 (see Section 10.1)

Table 6. 20: Summary statistics of time between consecutive visits (Days) from Screening Visit 1 to Visit 4², by treatment arm, for patients who underwent the most recent of the consecutive visits during/after¹ the Covid-19 pandemic (CHRONOS-B)

See output for Table 2. 7, but for patients in CHRONOS-B who underwent the most recent of the consecutive visits during/after¹ the Covid-19 pandemic.

¹Patients underwent the most recent of the consecutive visits during/after the Covid-19 pandemic if the date of visit of their most recent consecutive visit was after 05/03/2020 (see Section 10.1)

Table 6. 21: Proportions of patients, in each treatment arm, with a missing or delayed visit, for patients who underwent the visit before the Covid-19 pandemic (CHRONOS-A)

Visit ²		Focal	Radical	Total
Screening	Total	XXX	XXX	XXX
Visit 1	Delayed (n (%))	xxx (xx.x%)	xxx (xx.x%)	xxx (xx.x%)
	Missing (n (%))	xxx (xx.x%)	xxx (xx.x%)	xxx (xx.x%)
Visit 2	Total	xxx	xxx	XXX
	Delayed (n (%))	xxx (xx.x%)	xxx (xx.x%)	xxx (xx.x%)
	Missing (n (%))	xxx (xx.x%)	xxx (xx.x%)	xxx (xx.x%)
Visit 3	Total	xxx	xxx	XXX
	Delayed (n (%))	xxx (xx.x%)	xxx (xx.x%)	xxx (xx.x%)
	Missing (n (%))	xxx (xx.x%)	xxx (xx.x%)	xxx (xx.x%)

¹Patients underwent the visit before the Covid-19 pandemic if the date of visit was before 05/03/2020 (see Section 10.1)

²Patients are expected to have reached Visit 3 by the end of the feasibility phase

²Patients are expected to have reached Visit 3 by the end of the feasibility phase

²Patients are expected to have reached Visit 3 by the end of the feasibility phase

²Patients are expected to have reached Visit 3 by the end of the feasibility phase

STATISTICAL ANALYSIS PLAN: FEASIBILITY

CHRONOS

Table 6. 22: Proportions of patients, in each treatment arm, with a missing or delayed visit, for patients who underwent the visit during/after¹ the Covid-19 pandemic (CHRONOS-A)

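### The SAP's definition of a delayed visit counts early Visit 3s as delayed, cannot register a late Visit 2 dated as Section 6.7.2 says, and is undefined for Screening Visit 1 (Tables 6.21 to 6.24)

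*SAP*

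**What the plan says.** SAP Section 10.4 gives the rule: "A delayed visit is a visit which is outside of the visit window defined in the Visit Schedule (Section 6.7.2". It states no direction.

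Section 6.7.2 supplies the window and its origin. The window is "Time window for each visit will be +/- 4 weeks". The months in the schedule are counted from completion of treatment in each arm, with Visit 2 at month 0 and Visit 3 at month 3. On the origin it says "The end of treatment is defined as the final part of any intervention": the last fraction for radiotherapy, catheter removal for prostatectomy and focal therapy. Follow-up is counted from these time-points, "which will define the date of first follow-up visit (visit 2". Later follow-up is tied to the same date ("6 monthly visits until last visit 60 months after visit 2"). The screening column has no month.

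Section 10.4 also says "Treatment, for CHRONOS-A and CHRONOS-B, is recorded at Visit 2 (Treatment Visit".

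The output is in Section 10.6.2. Table 6.21 is titled "Proportions of patients, in each treatment arm, with a missing or delayed visit, for patients who underwent the visit before the Covid-19 pandemic" (CHRONOS-A). Table 6.22 is its during/after counterpart, and Tables 6.23 and 6.24 do the same for CHRONOS-B. Each has Total, Delayed and Missing lines for Screening Visit 1, Visit 2 and Visit 3. Periods are split by visit date, for example "Patients whose date of visit is before 05/03/2020" (Section 10.1).

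**The concern.** Section 9.5 lists missing or delayed visits among the measures of how the pandemic affected the feasibility phase, and Section 10.4 presents them as a summary of compliance. A reader will take a Delayed percentage to mean the share of visits that happened late. The rule does not measure that for any of the three visits. For Visit 3 it mixes early with late. For Visit 2 it compares the visit with its own date. For Visit 1 there is nothing to compare with.

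What is at stake is how one set of descriptive tables is read. A Visit 2 line near 0% in both periods could be taken as evidence that treatment visits kept to time, while other tables in the same section show longer waits. Visit 3s brought forward in one period would also appear as delay.

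**Working it through.** The documents state no figure for this point, so there is nothing to reproduce. The check applies the rule as written.

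**Inputs.** Half-width of window: 4 weeks = 28 days (6.7.2). Time zero: end of treatment = Visit 2 date (6.7.2). Targets: Visit 2 at month 0, Visit 3 at month 3, Visit 1 none (6.7.2). One month = 365.25 / 12 = 30.4375 days.

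**Rule.** Delayed if |visit day − target day| > 28.

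**Visit 3.** Target = 3 × 30.4375 = 91.3 days after Visit 2. Window = 91.3 − 28 to 91.3 + 28 = 63.3 to 119.3 days.

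| Visit 3 on day | Deviation (days) | True position | Scored by the rule |
|---|---|---|---|
| 56 | −35.3 | early | delayed |
| 62 | −29.3 | early | delayed |
| 64 | −27.3 | in window | not delayed |
| 119 | +27.7 | in window | not delayed |
| 120 | +28.7 | late | delayed |

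**Visit 2.** Visit day = 0 and target day = 0, so the deviation is 0. The time from randomisation does not enter the formula. With assumed mean waits of 45, 180 and 365 days (the documents give none), the Delayed proportion is 0.0% in each case.

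**Screening Visit 1.** With no target day, the expression cannot be evaluated.

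**Does the Visit 2 result survive other ways of dating treatment?** The SAP is not consistent here, so two variants were checked.

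- Section 8.3 uses the treatment-visit date as the start of treatment in the radical arm. If Visit 2 is dated d days before the end of treatment, its deviation is −d. Up to d = 28 it is not flagged. From d = 29 it is flagged, but because it is early relative to the end of treatment, not because treatment was late.
- The footnote to Table 2.9 records CHRONOS-B treatment at Visit 3, and Section 5.1 says Visit 2/3. If the treatment day were logged as Visit 3 and judged literally against month 3, the deviation would be 0 − 91.3 = −91.3 days. It would be flagged whatever the wait had been.

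So 0% is not certain under every reading, but neither variant turns the line into a measure of late treatment.

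**Extent.** Each of the four tables has three Delayed lines, 12 in all. The Visit 1 and Visit 2 lines (2 × 4 = 8) do not measure lateness, and the Visit 3 lines (4) mix early with late. The Total and Missing lines are not touched by this argument.

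**The case against.** The strongest reply is that treatment delay has its own endpoint. Section 9.5 compares the time from randomisation to treatment before and during/after the pandemic. Tables 6.11 and 6.12 (CHRONOS-A) and 6.15 and 6.16 (CHRONOS-B) give it in days by arm and period. Tables 6.17 to 6.20 add the Visit 1 to Visit 2 interval, with minimum and maximum, again by period. A reader might infer from the Visit 2 line that postponed surgery, radiotherapy or ablation is invisible in the Covid-19 analysis. The documents do not support that: a wait of several months would show in both sets of tables.

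Second, a Visit 2 result of exactly 0% depends on sites dating the visit at the end of treatment. Sections 6.7.2 and 8.3 and the footnote to Table 2.9 do not agree on this.

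Third, no decision rests on the proportion. Section 11 uses the recruitment rate, and Section 9.3 uses treatment and drug compliance. The delayed proportion has no threshold.

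All three replies stand, and they limit the point. They do not remove it: the rule still labels early visits as delayed, and the shells still carry two lines that the schedule cannot fill meaningfully. It is also fair to object to new target intervals from randomisation to treatment for each arm, since that interval is already reported in days. The fix does not need them.

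**Conclusion.** The point holds for the Delayed lines of Tables 6.21 to 6.24 and no further. As written, a Visit 3 before about day 63 is counted as delayed, the Visit 2 line cannot register late treatment when the visit is dated as Section 6.7.2 says, and the Screening Visit 1 line is undefined. The Visit 3 limits assume an average month length and move by a day or two with the calendar. The Visit 2 conclusion assumes Section 6.7.2 dating.

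A reader might go further and conclude that the Covid-19 analysis gives false reassurance about the treatment pathway, or that whole visit rows carry no information. Neither follows: the interval tables show treatment delay by period, and the Total and Missing lines are unaffected. Progression to the main stage is also unaffected. This is a correction to a planned descriptive output.

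**What to change.** 1. In SAP Section 10.4, define a delayed visit as one later than the upper limit of its window, and report visits before the lower limit separately as early.
2. In Tables 6.21 to 6.24, delete the Delayed lines for Screening Visit 1 and Visit 2. Add a note referring to Tables 6.11, 6.12, 6.15 and 6.16 for treatment delay. Keep the Total and Missing lines, and give Visit 3 both a Delayed and an Early line.
3. Reconcile the passages that date or number the treatment visit: end of treatment in Section 6.7.2 against start of treatment for the radical arm in Section 8.3, and Visit 2 in Section 10.4 against Visit 3 in the footnote to Table 2.9. This also matters for Tables 6.11 and 6.12, because Section 8.3 takes the radical-arm interval from the treatment-visit date.

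The cost is small edits to SAP wording and table shells. The visit dates are already among the SAP's variables (Section 8.3), and no new target interval is needed.
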